6.3.2. Mean Change from Baseline in the Number of Cluster Headache Attacks

The following 2nd and 3rd secondary efficacy endpoints will be analyzed based on the monthly average number of CH attacks using an MMRM method in a manner analogous to the analysis as described in Section 6.2.3.2.

- the mean change from baseline (run-in period) in the number of CH attacks during the 4-week period after administration of the first dose of the IMP, ie, based on week 0 to 4 data
- the mean change from baseline (run-in period) in the number of CH attacks during the 4-week period after administration of the third dose of the IMP, ie, based on week 8 to 12 data

Postbaseline data will include data from three 4-week analysis windows (weeks 1 to 4, weeks 5 to 8, and weeks 9 to 12) derived using the algorithm described in Section 6.1.3. Data will be

prorated to 28 days as the monthly average. CH attacks within each analysis window will be derived from the e-diary data as described in Section 6.1.1. Missing data handling methods are provided in Section 6.1.4.2

The analysis will be based on data from all three 4-week (monthly) analysis windows. Results for each endpoint will be subsetted from PROC MIXED outputs. For the 2nd secondary endpoint, the results from the first analysis window (weeks 1 to 4) will be presented; for the 3rd secondary endpoint, the results from the last analysis window (weeks 9 to 12) will be presented.

6.3.3. Mean Change from Baseline in the Weekly Average Number of Days with Use of Cluster-Specific Acute Headache Medications (Triptans and Ergot Compounds) During the 12-Week Period After Administration of the First Dose of the IMP

Use of triptans and ergot compounds for CH will be recorded in the e-diary. The 12-week period is the period from administration of the first dose of the IMP to the EOT/early withdrawal visit. The weekly average number of days with use of triptans or/and ergots for CH for a patient during 12-week period will be calculated and prorated to 7 days using formula [1B]. Missing data handling method is provided in Section 6.1.4.2.

Data will be analyzed using an ANCOVA method in a manner analogous to the primary endpoint as described in Section 6.2.2.

6.3.4. Mean Change from Baseline in the Weekly Average Number of Days Oxygen is Used to Treat Chronic Cluster Headaches During 12-week Period After Administration of the First Dose of the IMP

Use of oxygen will be recorded in the e-diary. The 12-week period is the period from administration of the first dose of the IMP to the EOT/early withdrawal visit. The weekly average number of days using oxygen for a patient during the 12-week period will be calculated and prorated to 7 days using formula [1B]. Missing data handling method is provided in Section 6.1.4.2.

Data will be analyzed using an ANCOVA method in a manner analogous to the primary endpoint as described in Section 6.2.2.

6.3.5. Patient-Perceived Satisfactory Improvement at 1, 4, 8, and 12 Weeks After Administration of the First Dose of the IMP Relative to Baseline

The PPSI scale will be completed in the e-diary at home at week 1(day 7) and in the investigational site tablet at the visits 2, 3, 4, and 5. Patients will mark the level of CH-associated pain and indicate the level of pain using the following scale compared with 4 weeks ago:

- 1 = Much worse
- 2 = Moderately worse
- 3 = Slightly worse
- 4 = Unchanged
- 5 = Slightly improved
- 6 = Moderately improved

- 7 = Much improved

PPSI will be defined as change in pain that corresponds with a minimal rating of “slightly improved” (Protocol Section 6.7). For analysis purpose, a dichotomous scale of “Responder” (scales 5 to 7) or “Non-responder” (scales 1 to 4) will be derived.

The percentage of patients in dichotomous scale of “Responder” or “Non-responder” at week 1, visit 3, 4, and 5 will be analyzed using a CMH method in a manner analogous to the first secondary endpoint as described in Section 6.3.1.

Modification to SAS code in Section 6.3.1: adding a ‘by’ statement for visit.

Raw scales will be summarized using descriptive statistics. A missing category will be presented if applicable.

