**Table 2: Study Procedures and Assessments**

Study period	Pretreatment period (including screening visit and run-in period)	Double-blind treatment period a			
Visit number	V1	V2	V3	V4	V5
Week number	Week -4 - 0	Week 0	Week 4	Week 8	Week 12
Procedures and assessments (completed before dosing, when applicable, unless otherwise noted)	Screening b	Baseline dose 1 day 0 (+3 days)	Visit 3 day 28 (±3 days)	Visit 4 day 56 (±3 days)	EOT or early withdrawal day 84 (±3 days)
Informed consent	X c				
Medical and psychiatric history	X				
Prior medication history	X				
Record demographic characteristics	X				
Inclusion and exclusion criteria	X	X			
Randomization		X			
Review study compliance		X	X	X	X
Physical examination, including weight and height d	X	X			X
Triplicate 12-lead ECG e	X	X			X
Vital signs measurement	X	X	X	X	X
Adverse events f	X	X g	X	X	X
Concomitant medication inquiry		X	X	X	X
Clinical laboratory tests h	X i	X	X	X	X
Serum β-HCG test j	X				X
Urine β-HCG test		X	X	X	
FSH k	X				
Provide electronic diary device l	X				

Study period	Pretreatment period (including screening visit and run-in period)	Double-blind treatment period a			
Visit number	V1	V2	V3	V4	V5
Week number	Week -4 - 0	Week 0	Week 4	Week 8	Week 12
Procedures and assessments (completed before dosing, when applicable, unless otherwise noted)	Screening b	Baseline dose 1 day 0 (+3 days)	Visit 3 day 28 (±3 days)	Visit 4 day 56 (±3 days)	EOT or early withdrawal day 84 (±3 days)
Enter cluster headache attack information in the electronic diary device m	X	X			X
Review electronic diary data		X	X	X	X
Return electronic diary device n					X
Blood samples for pharmacokinetics analysis o		X	X	X	X
Blood samples for ADA analysis p		X	X		X
Blood sample for pharmacogenomic analysis q		X			
Blood collection for serum, plasma, and RNA biomarker analysis f		X			X
Urine collection for biomarker analysis		X			X
HADS s		X	X		X
EQ-5D questionnaire s		X	X		X
SF-12 s		X	X		X
WPAI questionnaire s		X	X		X
Impact on Partner and Family questionnaire s,t		X	X		X
PPSI u		X	X	X	X
PGIC scale u			X	X	X
Provide wearable substudy sensor device and accessories		X			

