### **6.7. Patient-Perceived Satisfactory Improvement**

The PPSI was developed by [ten Klooster et al \(2006\)](#) for pain intensity and was adjusted for CH symptoms improvement. Patients will mark the level of CH-associated pain and indicate if pain is “much worse,” “moderately worse,” “slightly worse,” “unchanged,” “slightly improved,” “moderately improved,” or “much improved” compared with 4 weeks ago. PPSI will be defined as the change in pain that corresponds with a minimal rating of “slightly improved.”

The PPSI will be completed in the electronic diary device at home at week 1 and in the investigational site tablet at the time points detailed in [Table 2](#).

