### **9.5.2. Secondary Endpoints**

The secondary efficacy endpoints to further demonstrate efficacy are as follows:

- the proportion of patients with a  $\geq 50\%$  reduction from baseline (run-in period) in the monthly average number of CH attacks over the 12-week period after the administration of the first dose of the IMP, ie, based on week 0 to 12 data
- the mean change from baseline (run-in period) in the number of CH attacks during the 4-week period after administration of the first dose of the IMP, ie, based on week 0 to 4 data
- the mean change from baseline (run-in period) in the number of CH attacks during the 4-week period after administration of the third dose of the IMP, ie, based on week 8 to 12 data
- the mean change from baseline (run-in period) in the weekly average number of days with use of cluster-specific acute headache medications (triptans and ergot compounds) during the 12-week period after administration of the first dose of the IMP, ie, based on week 0 to 12 data
- the mean change from baseline (run-in period) in the weekly average number of days oxygen is used to treat CCH during the 12-week period after administration of the first dose of the IMP, ie, based on week 0 to 12 data
- assessment of patient's perceived improvement, as measured by the PPSI at 1, 4, 8, and 12 weeks after administration of the first dose of the IMP relative to baseline (day 0)

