
New section number due to removal of Section 6.2: Section 6.7<del>8</del>, Patient-Perceived Satisfactory Improvement
 
The PPSI was developed by ten Klooster et al (2006) and is composed of an unmarked 100 mm visual analog scale for pain intensity (VAS-P) and was adjusted for CH symptoms improvement with "no pain" and "unbearable pain" as anchors and a question regarding change in pain intensity. Patients will mark the level of CH-associated pain and indicate if pain is "much worse," "moderately worse," "slightly worse," "unchanged,"
	
Section 6.7, Patient-Perceived Satisfactory Improvement
 
The PPSI was developed by ten Klooster et al (2006) for pain intensity and was adjusted for CH symptoms improvement. Patients will mark the level of CH-associated pain and indicate if pain is "much worse," "moderately worse," "slightly worse," "unchanged," "slightly improved," "moderately improved," or "much improved" compared with 4 weeks ago. PPSI will be defined as the change in pain that corresponds with a minimal rating of
	
In the e-diary, a VAS cannot be used. Understanding that CH causes pain, the report to measure improvement or not is adapted for CH.

Original text with changes shown	New wording	Reason/Justification for change

<del>“unsatisfactory</del>slightly improved,”  <del>“satisfactory</del>moderately improved,” or “good to very good”  <del>much</del> improved” compared with <del>baseline (visit 2 [day 0])</del>4 weeks ago. PPSI will be defined as the change in pain <del>on the VAS-P</del> that corresponds with a minimal rating of <del>“satisfactory</del>slightly improved.”
	
“slightly improved.”
	

Section 6.8, Patient Global Impression of Change Scale
		

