1.2. Secondary Efficacy Endpoints

The secondary efficacy endpoints to further demonstrate efficacy are:

- the proportion of patients with a $\geq 50\%$ reduction from baseline (run-in period) in the monthly average number of CH attacks over the 12-week period after the administration of the first dose of the IMP, ie, based on week 0 to 12 data
- the mean change from baseline (run-in period) in the number of CH attacks during the 4-week period after administration of the first dose of the IMP, ie, based on week 0 to 4 data
- the mean change from baseline (run-in period) in the number of CH attacks during the 4-week period after administration of the third dose of the IMP, ie, based on week 8 to 12 data
- the mean change from baseline (run-in period) in the weekly average number of days with use of cluster-specific acute headache medications (triptans and ergot compounds) during the 12-week period after administration of the first dose of the IMP, ie, based on week 0 to 12 data
- the mean change from baseline (run-in period) in the weekly average number of days oxygen is used to treat chronic cluster headache (CCH) during the 12-week period after administration of the first dose of the IMP, ie, based on week 0 to 12 data
- assessment of patient's perceived improvement, as measured by the Patient-Perceived Satisfactory Improvement (PPSI) at 1, 4, 8, and 12 weeks after administration of the first dose of the IMP relative to baseline (day 0)

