7. MULTIPLE COMPARISONS AND MULTIPLICITY

Hochberg's step-up method will be implemented to test primary and secondary endpoints while controlling the overall type 1 error rate at 0.05.

The treatment comparisons will be for the fremanezumab 900-mg iv loading dose group versus placebo [H_{01}] and the fremanezumab 675-mg sc loading dose group versus placebo [H_{02}]. According to Hochberg step-up method, the rules of multiple comparisons for 2 null hypotheses for the primary endpoint are as follows:

1. If the resulting 2-sided p-values from both comparisons are ≤ 0.05 (reject both null hypotheses), then the next comparison of interest will be interpreted inferentially at the alpha level of 0.05 and statistical significance will be claimed for both active dose groups. Testing of secondary efficacy measures will be continued.
2. If the resulting 2-sided p-value from 1 of comparisons is > 0.05 (fail to reject the null hypothesis) and other resulting 2-sided p-value is ≤ 0.025 ($\frac{\alpha}{2} = 0.025$; reject the null hypothesis), then the result from the comparison with p-value ≤ 0.025 will be interpreted inferentially at the alpha level of 0.05, and statistical significance will be claimed for this active dose group. No further comparisons will be interpreted inferentially.
3. If the resulting 2-sided p-value from both comparisons are > 0.05 (fail to reject both null hypotheses), then no statistical significant will be claimed and no comparisons will be interpreted inferentially.

If the resulting 2-sided p-values from both comparisons for the primary endpoint are ≤ 0.05 (reject both hypotheses; case 1 as described above), testing of secondary efficacy measures will proceed at an error rate of 0.05 in the sequential manner as specified in Section 1.2. The same testing rules as described above will be followed. This process will continue either until all comparisons of interest for secondary endpoints are interpreted inferentially or until the point at which the resulting 2-sided p-value for a comparison of interest is > 0.05 . At the point where a 2-sided p-value > 0.05 , the testing process stops. No further comparisons will be interpreted inferentially.

For the last secondary endpoint (PPSI assessments), only the assessment at week 12 will be included in the multiple comparisons.

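### The PPSI endpoint is defined against day 0 but rated against four weeks earlier, so the confirmatory week-12 test would measure change since about day 56

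*SAP*

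**What the plan says.** The endpoint definition is anchored to the first dosing visit. SAP 1.2 lists the PPSI at weeks 1, 4, 8 and 12 after "administration of the first dose of the IMP relative to baseline (day 0"). Protocol 2.1 and 9.5.2 say the same; the 9.5.2 wording is "after administration of the first dose of the IMP relative to baseline (day 0"). The heading of SAP 6.3.5 repeats the anchor: "Weeks After Administration of the First Dose of the IMP Relative to Baseline".

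The description of the item is anchored differently. Protocol 6.7 has the patient rate pain "compared with 4 weeks ago", and the body of SAP 6.3.5 has the patient "indicate the level of pain using the following scale compared with 4 weeks ago". SAP 6.3.5 then dichotomises the raw seven-point rating. Scores 5 to 7 are responders; scores 1 to 4 are non-responders, and 4 is the no-change category. The flag is analysed by visit with a CMH test.

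On multiplicity, SAP 7 states that for the PPSI "only the assessment at week 12 will be included in the multiple comparisons".

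**The concern.** Both anchors cannot hold at week 12. The derivation contains no step that links the rating back to day 0, so the endpoint label and the quantity analysed differ. The conflict matters most at week 12, because that is the only PPSI result that can be interpreted inferentially.

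Protocol 5.3.1 gives the loading dose to obtain a rapid response and the monthly doses to maintain it. An early gain that is then held is therefore the pattern the sponsor hopes to see. Under a four-week recall, such a patient would report no change at week 12 and be a non-responder. Conversely, a patient who worsened up to week 8 and then partly recovered could be a responder. In both cases the result would be reported as improvement, or lack of it, from baseline, which is not what was rated.

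**Working it through.** **The plan's own figure.** The documents give no power, sample size or expected rate for the PPSI. The only sample-size figure is for the primary endpoint (SAP 2.4: difference 4, SD 8, two-sided 0.05, 90% power, 86 per group). It reproduces: n = 2 × (1.960 + 1.282)² × (8/4)² ≈ 84.1, so 85 per group; power at 86 per group is 0.906; 258 / (1 − 0.14) = 300. None of this depends on the PPSI anchor.

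**Inputs for the check.** Visit days and windows come from Protocol Table 2: day 28 (±3), day 56 (±3), and "EOT or early withdrawal day 84 (±3 days") for week 12. Week 1 is day 7 (SAP 6.3.5 and Protocol Appendix B). The recall length is 28 days (Protocol 6.7 and the body of SAP 6.3.5).

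**Formula.** Reference day = assessment day − 28.

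| Assessment | Nominal day | Reference day | With ±3-day window |
|---|---|---|---|
| Week 1 | 7 | 7 − 28 = −21 (run-in) | no window stated |
| Week 4 | 28 | 28 − 28 = 0 | −3 to 3 |
| Week 8 | 56 | 56 − 28 = 28 | 25 to 31 |
| Week 12 | 84 | 84 − 28 = 56 | 53 to 59 |

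Days use the protocol's numbering, with first dose on day 0. In the SAP's numbering, with first dose on day 1, the week-12 reference is about day 57. Appendix B gives only a +3-day window for the week-12 visit, which would narrow the range to 56 to 59.

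Only the week-4 rating refers back to day 0. The week-12 rating refers back to about visit 4, when the third dose is given. Of the 84 treatment days, 28 (28/84 = 33%) fall after that reference point. The other 56 (56/84 = 67%), which contain the loading dose and the second dose, fall before it.

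**Does anything reconcile the anchors?**
- The SAP introduction says the SAP prevails over the protocol. That does not help, because SAP 1.2 and the body of SAP 6.3.5 disagree with each other.
- SAP 17 lists no changes from the protocol.
- The PPSI is also completed at visit 2 before dosing, but SAP 6.3.5 does not use that rating as a reference; the responder flag uses each later rating alone. A rating of change since day 0 also has little meaning on day 0 itself, whereas a four-week recall does. This fits a rolling recall but does not prove the device wording.
- The PGIC (Protocol 6.8, SAP 6.4.9.6) is explicitly anchored to study start, so a fixed anchor was written where one was intended.

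**History only.** The Amendment 01 log (Protocol 16.2) shows the item description losing its anchor to "baseline (visit 2 [day 0"]) and gaining the four-week one, before any patient was enrolled. The conflict described here is in the current text and does not rest on that log.

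**The case against.** The strongest reply is that this is a labelling slip. SAP 6.3.5 fully specifies the scale, the cut-off, the test and the time points, so a programmer would code it only one way. No alpha, sample size or decision rule changes. The PPSI is also the sixth and last secondary endpoint. It is reached only if both comparisons are at or below 0.05 on the primary and on each of the five earlier secondaries: (1 + 5) × 2 = 12 comparisons. The amendment history suggests the four-week recall was adopted deliberately, leaving stale endpoint wording. The harm also assumes that the screens match the description and that patients apply a four-week recall literally.

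Much of this stands as a limit on weight. The impact is small and conditional, and the 33%/67% split is a calendar description rather than a measure of how much treatment effect is captured. It does not remove the conflict. An analysis can be programmed without ambiguity and still answer a different question from the one its endpoint states, and this result would carry an inferential claim about change from baseline.

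Two further points are fair and bear on the remedy. Protocol 2.1 and 9.5.2 carry the same day 0 wording as SAP 1.2. And if the device does use a day 0 anchor, the meaning of the predose visit 2 rating needs explaining.

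**Conclusion.** The concern holds. The current protocol and SAP define the PPSI endpoint against day 0 and describe a rating against four weeks earlier, and no text reconciles them. Followed as written, the one confirmatory PPSI result would be reported as improvement from baseline while measuring change since about day 56 (53 to 59).

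The textual conflict is certain. The consequence rests on the tablet and e-diary wording matching the description, which the documents do not show. The effect on responder rates or power cannot be quantified and could go either way, because the documents give no PPSI rates, no share of patients who plateau and no rate of new improvement after the third dose. The primary endpoint, the earlier secondary endpoints and the type 1 error rate are unaffected, and PPSI results at weeks 1, 4 and 8 lie outside the testing sequence. It should be fixed, but it does not threaten the trial's main conclusion.

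**What to change.** Before unblinding, confirm the recall wording shown to patients on the site tablet and the e-diary.

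- **If it is four weeks:** redefine the endpoint in SAP 1.2 and 6.3.5 as perceived change over the previous four weeks and remove the day 0 anchor. Limit the week-12 confirmatory claim to change since about week 8. Identify week 4 as the only assessment whose reference point is day 0, reported outside the sequence. Record the departure from Protocol 2.1 and 9.5.2 in SAP 17. Moving the confirmatory time point to week 4 is open to the sponsor but not required.
- **If it is day 0:** correct Protocol 6.7 and the body of SAP 6.3.5, and say how the predose visit 2 rating is to be read.

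The cost is one check of the device screens and a few sentences, with no new data. The downside is that a four-week recall leaves a narrower confirmatory claim, covering late change only. The week-12 PGIC is anchored to study start, but it is exploratory and rates overall health and well-being, so it can support the claim but not replace it.

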6.4. Exploratory Efficacy Endpoints and Analysis

Exploratory efficacy endpoints are listed in Section 1.5. Analyses will be based on the FAS.

As exploratory analyses, endpoints analyzed using an ANCOVA method will be also analyzed using MMRM method in a manner analogous to the analysis as described in Section 6.2.3.2.

6.4.1. Proportion of Patients with $\geq 50\%$, 75%, or 100% Reduction from Baseline in Number of CH Attacks During the 12-Week Period (First 3 Exploratory Efficacy Endpoints)

The following exploratory efficacy endpoint will not be analyzed since the result would be the same as these from the first secondary endpoint (≥ 50 reduction in monthly average). Note, the calculation of a proportion based on the weekly average or monthly average would yield the same result.

- proportion of patients with $\geq 50\%$ reduction from baseline (run-in period) in the weekly average number of CH attacks during the 12-week period after administration of the first dose of the IMP, ie, based on week 0 to 12 data

The following exploratory efficacy endpoints will be analyzed using a CMH method in a manner analogous to the first secondary endpoint as described in Section 6.3.1. The proportion of reductions will be calculated based on **monthly average number** of CH attacks to be consistent with the calculation of the first secondary endpoint.

- proportion of patients with $\geq 75\%$ reduction from baseline (run-in period) in the weekly average number of CH attacks during the 12-week period after administration of the first dose of the IMP, ie, based on week 0 to 12 data
- proportion of patients reaching 100% reduction in the number of CH attacks during the 12-week period after administration of the first dose of the IMP, ie, based on week 0 to 12 data

The 12-week period is the period from administration of the first dose of the IMP to the EOT/early withdrawal visit. CH attacks within the 12-week period will be derived from the e-diary data as described in Section 6.1.1 and prorated to 28 days using formula [1A]. Missing data handling methods are provided in Section 6.1.4.2.

The proportion of reduction for a patient will be calculated using formula [2]. Responders will be those with $\geq 75\%$ or 100% reduction, respectively.

The monthly analyses will be presented.

6.4.2. Mean Change from Baseline in the Number of CH Attacks During Weeks 1, 2, 3, 4, 8, and 12 After Administration of the First Dose of the IMP

This exploratory efficacy endpoint will be analyzed using an MMRM in a manner analogous to the analysis as described in Section 6.2.3.2.

Postbaseline data will include data from twelve 1-week analysis windows derived using the algorithm described in Section 6.1.3. Missing data handling methods are provided in Section 6.1.4.3. If days with e-diary data in a 1-week analysis window are more than 7, CH attacks for the analysis window will be prorated to 7 days using formula [1B].

Analyses will be based on data from all 12 analysis windows. Results for weeks 1, 2, 3, 4, 8, or 12 will be subsetted from PROC MIXED outputs afterwards.

LSMEANS statement in PROC MIXED will be changed to:

LSMEANS TRTP*ATPTN/ DIFF CL ALPHA=0.05;

6.4.3. Mean Change from Baseline in the Number of CH Attacks During the 8-Week Period (Weeks 0 to 8) After Administration of the First Dose of the IMP

This exploratory efficacy endpoint will be analyzed using an MMRM in a manner analogous to the analysis as described in Section 6.2.3.2.

Postbaseline data will include data from analysis windows of weeks 1 to 4 and weeks 5 to 8 derived using the algorithm described in Section 6.1.3. Missing data handling methods are provided in Section 6.1.4.2. The overall results from PROC MIXED will be presented.

LSMEANS statement in PROC MIXED will be changed to:

LSMEANS TRTP / DIFF CL ALPHA=0.05;

6.4.4. Mean Change from Baseline in the Number of CH Attacks During the 4-Week Period (Weeks 4 to 8) After Administration of the Second Dose of the IMP

The exploratory efficacy endpoints will be analyzed based on the monthly average number of CH attacks using an MMRM method in a manner analogous to the analysis as described in Section 6.3.2.

The analysis will be done in the same PROC MIXED procedure as described in Section 6.3.2. The results from the second analysis window (weeks 5 to 8) will be subsetted from the output of the PROC MIXED and will be presented.

6.4.5. Change from Baseline in the Severity of CH Attacks (Mild, Moderate, Severe and Very Severe) During Weeks 1, 2, 3, 4, 8, and 12 After Administration of the First Dose of the IMP

Pain severity for each CH attack will be recorded in the e-diary as follows:

1 = Mild

2 = Moderate

3 = Severe

4 = Very Severe

The analysis will be based on daily average derived from the numerical rating (1, 2, 3, or 4). If there is more than 1 CH attack for a day, the worst severity of CH attacks for that day will be used for the analysis. For patients who do not have CH attacks in a day, the severity rating for that day will be set to 0.

The weekly average severity of CH attacks will be calculated as follows:

$$\frac{\sum \text{most severe CH attack per day during a week}}{\text{Number of days with assessments recorded in the eDiary during a week}}$$

Change from baseline in the severity of CH attacks will be analyzed based on the calculated weekly average severity rating using an MMRM in a manner analogous to the analysis as described in Section 6.2.3.2. Postbaseline data will include data from all twelve 1-week analysis windows.

Analyses will be based on data from all 12 weekly analysis windows. Results for weeks 1, 2, 3, 4, 8, or 12 will be subsetted from PROC MIXED outputs afterwards.

LSMEANS statement in PROC MIXED will be changed to:

LSMEANS TRTP*ATPTN/ DIFF CL ALPHA=0.05;

6.4.6. Mean Change from Baseline in the Weekly Average Number of Days with Use of any Acute Headache Medications During the 12-Week Period After Administration of the First Dose of the IMP

Use of any acute headache medication will be recorded in the e-diary. The 12-week period is the period from administration of the first dose of the IMP to the EOT/early withdrawal visit. The weekly average number of days with use of any acute headache medication (triptan, ergot, opioids, or butalbital) for CH within the 12-week period for a patient will be calculated and prorated to 7 days using formula [1B]. The missing data handling method for analysis of mean change from baseline is provided in Section 6.1.4.2.

Data will be analyzed using an ANCOVA method in a manner analogous to the primary endpoint as described in Section 6.2.2.

